### Collection of Pregnancy Information

#### Male participants with partners who become pregnant

- The Investigator will attempt to collect pregnancy information on any male participant's female partner, who becomes pregnant while the participant is in this study. This applies only to participants who receive study intervention.
- After obtaining signed consent from the pregnant female partner directly, the Investigator will record the pregnancy information on the appropriate form and submit it to the Sponsor within 24 hours of learning of the pregnancy. The female partner will also be followed to determine the outcome of the pregnancy. Information on the status of the mother and child will be forwarded to the Sponsor. Generally, the follow-up will be no longer than 6 to 8 weeks following the estimated delivery date. Any termination of the pregnancy will be reported regardless of fetal status (presence or absence of anomalies) or indication for the procedure.

#### Female Participants who become pregnant

- The Investigator will collect pregnancy information on any female participant who becomes pregnant while she is in the study. The initial information will be recorded on the appropriate

form and submitted to the Sponsor within 24 hours of learning of the pregnancy.

- The participant will be followed to determine the outcome of the pregnancy. The Investigator will collect follow-up information on the participant and the neonate, and the information will be forwarded to the Sponsor. Generally, follow-up will not be required for longer than 6 to 8 weeks beyond the estimated delivery date. Any termination of pregnancy will be reported, regardless of fetal status (presence or absence of anomalies) or indication for the procedure.
- While pregnancy itself is not considered to be an AE or SAE, any pregnancy complication or elective termination of a pregnancy for medical reasons will be reported as an AE or SAE.
- A spontaneous abortion (occurring at <22 weeks gestational age) or stillbirth (occurring at >22 weeks gestational age) is always considered to be an SAE and will be reported as such.
- Any post-study pregnancy related SAE considered reasonably related to the study intervention by the Investigator will be reported to the Sponsor as specified in Section 8.3.4. While the Investigator is not obligated to actively seek this information in former study participants, he or she may learn of an SAE through spontaneous reporting.
- Any female participant who becomes pregnant while participating in the study will discontinue study intervention or be withdrawn from the study.

### **8.3.6                   Disease-Related Events and/or Disease-Related Outcomes Not Qualifying as AEs or SAEs**

The following disease-related events are common in participants with metastatic colorectal cancer and can be serious/life threatening:

- Progressive disease

Because these events are typically associated with the disease under study (e.g., progressive disease), they will not be reported according to the standard process for expedited reporting of SAEs even though the event may meet the definition of a SAE. These events will be recorded on the applicable eCRF page within the appropriate time frame.

However, if either of the following conditions applies, then the event will be recorded and reported as an SAE (instead of a disease-related events):

- The event is, in the Investigator's opinion, of greater intensity, frequency, or duration than expected for the individual participant.

OR

- The Investigator considers that there is a reasonable possibility that the event was related to study intervention.

### **8.3.7                   Adverse Events of Special Interest**

For this study, AESIs include only the following:

- AEs suggestive of drug-induced liver injury including hepatic/liver failure and hepatitis (non-infectious) are considered AESIs.

AESIs will be reported to the Sponsor (or delegate) in an expedited manner as described in [Appendix 7](#).

### **8.4                      Treatment of Overdose**

For this study, any dose of tepotinib or cetuximab greater than the dose that is defined in this clinical study protocol will be considered an overdose.

[figure not shown]
The Sponsor does not recommend specific treatment for an overdose.

Even if not associated with an AE or a SAE, any overdose is recorded in the eCRF and reported to global patient safety in an expedited manner. Overdoses are reported on a SAE and Overdose Report Form, following the procedure in [Appendix 7](#).

## 8.5

### Pharmacokinetics

CCI

[figure not shown]

CCI

- Liquid biopsy (whole blood) and/or tissue biopsy samples will be collected to test *MET* amplification that should be detected by a positive test with appropriate regulatory status (collected after disease progression of the previous anti-EGFR therapy). Local *MET* amplification testing of tissue and/or Sponsor overseen central liquid biopsy sample testing will be allowed for enrolment only with an assay with appropriate validation and regulatory status. If local *MET* amplification tests do not have the appropriate regulatory status or if the samples are not analyzed locally, central confirmation of *MET* amplification is offered and needed before enrolling. Participants should have shown benefit from the previous anti-EGFR therapy by CR or PR, both at least for 4 months or SD for at least 6 months prior to disease progression.

CCI

CCI

## 8.9 Immunogenicity Assessments

Whole blood samples of approximately 3.5 mL will be collected for detection of antibodies against cetuximab in serum. Collection times are specified in the SoA (Section 1.3).

The detection of antibodies to cetuximab will be performed using a validated immunoassay method with tiered testing of screening, confirmatory and titration. Confirmed positive antibodies may be further characterized.

CCI

Details on processes for collection and handling of these samples are in a Laboratory Manual. Retention time and possible analyses of samples after the end of study are specified in the respective ICF.

## **8.10 Medical Resource Utilization and Health Economics**

Not applicable. There is no health economic objective, nor any resource utilization outcomes measures for this study.

## **9 Statistical Considerations**

Analysis of all data will be performed by the Sponsor or its designee. The results of all study parts will be reported in the clinical study report. Analyses will be performed separately for each cohort. Details of the analysis of safety, efficacy, PK, and biomarker data will be presented in the Integrated Analysis Plan (IAP), which will be finalized before the database is locked for analysis.

### **9.1 Statistical Hypotheses**

No formal statistical hypothesis will be tested, as the study is designed to be exploratory.

### **9.2 Sample Size Determination**

The number of participants to be screened is expected to be around 342 participants to account for the described heterogeneity for *MET* amplification in the planned setting (Pietrantonio 2017; Pietrantonio 2015; Raghav 2016; Liu 2019; Mohan 2014; Siravegna 2015; Morelli 2014; Montagut 2018; LC-SCRUM, ASCO 2019 [Nakamura 2019]).

In total, a maximum of 48 participants are planned to be assigned to study intervention such that approximately 22 (Cohort A) and 20 (Cohort B) participants will be treated at RP2D. The 42 participants will be under the same dose level. The sample size calculation of 42 participants is based on the full analysis set (FAS).

The aim is to have 22 participants treated with the RP2D of tepotinib for 2L line treatment (Cohort A) and 20 participants treated with the RP2D for the 3L+ treatment (Cohort B) with at least 6 participants in the safety run-in period, irrespective of cohort.

It is anticipated that 6 eligible participants irrespective of therapy line, will be enrolled into the first part of the study for the determination of RP2D of tepotinib depending on DLTs observed. If 250 mg tepotinib is to be used the number of participants enrolled for the determination of RP2D will increase up to 12 (See Section 9.4.2.1).

#### **2nd Line treatment (Cohort A):**

A sample size of 22 participants treated with the RP2D of tepotinib (including those RP2D-dosed participants from the safety run-in), is chosen for the following reasons:

The probability to observe 5 or more responders (confirmed CR or PR) out of 22 treated participants ( $5/22 = 22.7\%$  response rate) is 80.8% under the assumption of a true response rate of 30% (relevant clinical effect); whereas, if the true responder rate is 10% (non-relevant clinical effect regarding further development of this combination therapy in this indication), the probability to observe 5 or more responders is 5.7%. In these calculations, a futility analysis is considered which will be performed after 12 participants are enrolled and monitored without stopping recruitment of further participants into this study. If there are less than 2 responders within the first 12 treated participants, the enrollment of 2L participants for the study will be stopped for futility. Under the assumption of a true rate of 30%, the probability of a false stop will be 8.5%; whereas in case of a true rate of 10%, the probability of a correct stop will be 65.9%.

The overall threshold of >20% responders at the end of the study was set based on the development consideration for 2L where bevacizumab + chemotherapy showed a response rate of 22.7% (Giantonio 2007).

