## 1.2 Schema

A high-level schedule of visits / assessments is shown in Section 1.3. Number of participants to be screened is described in Section 9.2.

Abbreviations: 2L = 2nd Line; 3L+ = 3rd Line+; DLT = Dose Limiting Toxicity; QD = once daily; RP2D = Recommended Phase II Dose; SMC = Safety Monitoring Committee; US = United States.

- a Required loading dose at an initial dose of 400 mg/m^2 body surface area if participant received the following:
  - Panitumumab as prior line
  - Cetuximab as prior line and last dose was more than 3 weeks ago.No loading dose required if participant received cetuximab as prior line and last dose was given up to 3 weeks ago.
- b The 250 mg once daily dose is the standard dose reduction. If a participant still does not tolerate the 250 mg once daily dose, or the AE does not resolve following treatment interruption, permanent treatment discontinuation or other dosing schemas should be discussed with the Sponsor.
- c Cohort A will include participants from outside the US. A futility analysis is considered which will be performed after 12 participants are enrolled and monitored without stopping recruitment of further participants into this study.
- d After the safety run-in period, at least 16 additional participants will be enrolled at the RP2D expansion in Cohort A, in addition to the 6 participants completing the safety run-in at RP2D.
- e Cohort B will include US participants only.

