#### 3rd Line+ treatment (Cohort B):

A sample size of 20 participants treated with the RP2D of tepotinib (including those RP2D-dosed participants from the safety run-in), is required, so that the probability to observe 2 or more responders (confirmed CR or PR) out of 20 treated participants ( $2/20 = 10.0\%$  response rate) is 82.4% under the assumption of a true response rate of 15% (relevant clinical effect); whereas, if the true response rate is 2.5% (non-relevant clinical effect regarding further development of this combination therapy in this indication), the probability to observe 2 or more responders is 8.8%. No futility analysis is planned here due to the low rate of expected responders in the 3L+ setting.

The threshold of  $\geq 10\%$  for 3L+ was set based on data for regorafenib or trifluridine/tipiracil, which showed a response rate of maximum 4% (Li 2015, Mayer 2015).

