Participants are defined as having an Objective Response (OR) if they achieved either a BOR of confirmed CR or confirmed PR according to RECIST v1.1 as assessed by the investigator, from first administration of study treatment to first observation of PD.

Participants who do not have an on-treatment radiographic tumor assessment due to early progression, who receive anti-tumor treatments other than the study treatments prior to reaching confirmed CR or

PR, or who die, progress, or drop out for any reason prior to reaching confirmed CR or PR will be counted as non-responders in the assessment of OR. Each participant will have an objective response status (0: 'no OR'; 1: 'OR'). OR rate (ORR) is the proportion of participants with OR in the analysis set. No formal statistical hypotheses will be tested.

The number and percentage of participants with BOR of confirmed CR, confirmed PR, SD, PD, and NE will be tabulated.

The confirmed ORR by cohort and assigned dose level of tepotinib will be presented along with the two-sided 95% CI using the Clopper-Pearson method (1934) (exact CI for a binomial proportion as computed by default by the SAS FREQ procedure using the EXACT option).

A spider plot will show the participant profiles of the sum of target lesion diameters (sum of longest diameters for non-nodal lesions, short axis for nodal lesions) over time (presenting all participants on the same graph). In addition, a waterfall plot will show the change in sum of target lesion diameters between baseline and the best post-baseline assessment for each participant.

Time to and duration of response by investigator assessment for every participant will be plotted using a swimmer plot. Color coded symbols will be used to show the time of the following events: CR, PR, PD, death, ongoing response and end of treatment.

Estimand Attributes

Endpoint:

- OR according to RECIST 1.1 assessed by Investigator prior to further anti-cancer therapy and progression

Population:

- Participants with *RAS/BRAF* wild-type left-sided metastatic colorectal cancer (mCRC) having acquired resistance to anti-EGFR antibody targeting therapy due to *MET* amplification

Treatment:

- Tepotinib combined with cetuximab

Intercurrent Event Strategy:

- Discontinuation of treatment (treatment-policy strategy, i.e. regardless of the intercurrent event)

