14.1.3 Futility Analysis

Best Overall Response (BOR) as described above will be reported for the first 12 participants, in Cohort A. If there are less than 2 responders (confirmed CR or PR) the enrollment of 2nd line participants for the study might be stopped for futility.

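### Do the end-of-study response thresholds in protocol 9.2 need to be carried into the SAP in a single form?

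*Protocol*

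**What the plan says.** Protocol 9.2 gives each cohort a threshold in two forms.

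- **Cohort A (second line).** The count appears in "The probability to observe 5 or more responders (confirmed CR or PR) out of 22 treated participants", which 9.2 itself converts to 22.7%. The percentage follows: "The overall threshold of >20% responders at the end of the study was set based on the development consideration for 2L". The paragraph also contains an interim look: fewer than 2 responders among the first 12 stops second-line enrolment.
- **Cohort B (third line and later).** The count appears in "the probability to observe 2 or more responders (confirmed CR or PR) out of 20 treated participants", converted to 10.0%. The percentage is at least 10%, a threshold that "for 3L+ was set based on data for regorafenib or trifluridine/tipiracil, which showed a response rate of maximum 4" per cent.

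The sizes are not exact: "approximately 22 (Cohort A) and 20 (Cohort B) participants will be treated at RP2D". Note d to the schema (protocol 1.2) says that "at least 16 additional participants will be enrolled at the RP2D expansion in Cohort A", on top of the 6 who complete the run-in at the RP2D.

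On analysis, protocol 9.1 states that no formal hypothesis is tested. Protocol 9.4.1 and SAP section 9 call all analyses descriptive, with no significance level. SAP 14.1.1 plans the following: "The confirmed ORR by cohort and assigned dose level of tepotinib will be presented along with the two-sided 95% CI", using Clopper-Pearson. The only response cut-off in the SAP is the interim one (6.2 and 14.1.3): "If there are less than 2 responders (confirmed CR or PR) the enrollment of 2nd line participants" may be halted. Neither final threshold appears there.

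**The concern.** Objective response is the primary endpoint, judged by the investigator in an open-label study. Section 9.2 labels the assumed true rates as clinically relevant or not relevant for further development, so its thresholds read like a go/no-go rule. A rule of that kind is best fixed before the counts are known. Here the SAP takes up the interim cut-off and is silent on the final one, and 9.2 states the final one in two forms that are not equivalent at every cohort size.

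Cohort B sits at the upper edge of the range where the forms agree, so a single extra treated participant separates them. That is plausible. The run-in may draw on either cohort, participants who are not DLT-evaluable are replaced, and anyone dosed stays in the full analysis set. At 21 participants, exactly 2 responders could be described as meeting the threshold or as missing it, depending on which form is chosen afterwards.

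**Working it through.** **Inputs (protocol 9.2).** Cohort A: n = 22, at least 5 responders, interim stop if fewer than 2 of the first 12, true rates 10% and 30%, percentage form above 20%. Cohort B: n = 20, at least 2 responders, true rates 2.5% and 15%, percentage form at least 10%.

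**Step 1. Reproduce the plan's probabilities (exact binomial).**

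Cohort A, with X₁ responders in the first 12 and X₂ in the next 10: P(pass) = Σ over x ≥ 2 of P(X₁ = x) × P(X₂ ≥ 5 − x).

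| Cohort A quantity | At 10% | At 30% | Stated in 9.2 |
|---|---|---|---|
| Interim stop, P(X₁ ≤ 1) | 65.90% | 8.50% | 65.9%, 8.5% |
| Pass, with the look | 5.69% | 80.84% | 5.7%, 80.8% |
| Pass, ignoring the look | 6.2% | 83.5% | not stated |

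The stated figures therefore include the look.

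Cohort B: P(X ≥ 2) = 1 − (1 − p)²⁰ − 20p(1 − p)¹⁹.
- At 15%: 1 − 0.0388 − 0.1368 = 0.8244 (stated 82.4%).
- At 2.5%: 1 − 0.6027 − 0.3091 = 0.0882 (stated 8.8%).

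All the figures match.

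**Step 2. Compare the two forms at the planned sizes.**
- Cohort A: 4/22 = 18.2% fails both; 5/22 = 22.7% passes both.
- Cohort B: 1/20 = 5.0% fails both; 2/20 = 10.0% passes both.

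At 22 and 20 they are one rule.

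**Step 3. Find where they separate.** Take the smallest r with r/n > 0.20 (A) or r/n ≥ 0.10 (B).

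| Cohort | n | Needed by percentage | Needed by count |
|---|---|---|---|
| A | 16–19 | 4 | 5 |
| A | 20–24 | 5 | 5 |
| A | 25–28 | 6 | 5 |
| B | 11–20 | 2 | 2 |
| B | 21–26 | 3 | 2 |

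Cohort A needs a departure of 3 or more in either direction before the forms differ. Cohort B agrees for any shortfall down to 11 and separates only on over-enrolment.

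**Step 4. Size of the difference where they separate.** The Cohort A figures keep the interim look, as 9.2 does.

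| Case | True rate | Pass by count | Pass by percentage |
|---|---|---|---|
| B, n = 21 | 15% | 84.5% | 63.0% |
| B, n = 21 | 2.5% | 9.6% | 1.5% |
| A, n = 19 | 30% | 70.8% | 84.0% |
| A, n = 19 | 10% | 3.4% | 10.5% |

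In Cohort B the disputed outcome is exactly 2 of 21. Its probability is 84.5% − 63.0% = 21.5% at a true 15%, given that n is 21. The documents supply no probability that n reaches 21.

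**Step 5. What would be reported.** Under SAP 14.1.1 the exact 95% intervals are:
- 2/20 = 10.0%, 1.2% to 31.7%
- 2/21 = 9.5%, 1.2% to 30.4%

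The evidence is practically the same on either side of the split.

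**The case for a change.** The strongest argument for a change is that calling the study exploratory does not settle how a threshold is read. The SAP says it specifies all analyses and that unplanned ones will be identified as such in the study report. A comparison with the 9.2 threshold would then have unclear standing. In Cohort B the choice of form shifts the pass probability at a true 15% by more than 20 percentage points once n is 21. One sentence written before database lock would remove the ambiguity at almost no cost.

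The facts in this stand: the SAP is silent, and the forms do differ away from plan. The inference that the plan must change does not.

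- Section 9.2 offers the thresholds as reasons for the sample sizes and as development considerations. A sponsor's development decision need not be an SAP analysis. The interim cut-off is in the SAP because it bears on enrolment, and even there the SAP words stopping as a possibility where the protocol words it as certain.
- Section 9.2 links the two forms by arithmetic at the planned sizes, so it contains no contradiction.
- The schema note is weak evidence for a Cohort A as small as 19. If all 6 run-in participants come from Cohort A, 16 + 6 = 22 is a minimum. A smaller cohort is possible only if some of the run-in is in Cohort B, or if enrolment falls short or ends early.
- The proposed sentence could equally say that the thresholds are for planning only, which shows that no analysis turns on it.

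It can also be said that 9.2 gives pass probabilities at only two true rates per cohort, and not at the rates of the cited therapies. More rows could be tabulated, but 9.2 does say what its lower rates mean (an effect not relevant for further development), and the extra rows would not alter the design.

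**Conclusion.** No change is called for. The two forms coincide at the planned 22 and 20 and over 20 to 24 (Cohort A) and 11 to 20 (Cohort B), and no figure in 9.2 is wrong. The difference is real if Cohort B treats 21 or more (84.5% against 63.0% at a true 15%, for n = 21) or if Cohort A falls outside 20 to 24. Even then it affects only a descriptive label, because the count, the response rate and its exact interval are reported regardless, and a reader can set them against either form.

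This rests on two things: the study remains descriptive, as protocol 9.1 and 9.4.1 and SAP section 9 state, and the final cohort sizes stay near plan. If the sponsor wants to tidy the text, a note in SAP 14.1.1 could say that the thresholds are for planning only, or that the percentage is compared descriptively with the observed rate at the actual n. That is optional wording which leaves the sample size, interim rule and estimation as they are.

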#### 3rd Line+ treatment (Cohort B):

A sample size of 20 participants treated with the RP2D of tepotinib (including those RP2D-dosed participants from the safety run-in), is required, so that the probability to observe 2 or more responders (confirmed CR or PR) out of 20 treated participants ( $2/20 = 10.0\%$  response rate) is 82.4% under the assumption of a true response rate of 15% (relevant clinical effect); whereas, if the true response rate is 2.5% (non-relevant clinical effect regarding further development of this combination therapy in this indication), the probability to observe 2 or more responders is 8.8%. No futility analysis is planned here due to the low rate of expected responders in the 3L+ setting.

The threshold of  $\geq 10\%$  for 3L+ was set based on data for regorafenib or trifluridine/tipiracil, which showed a response rate of maximum 4% (Li 2015, Mayer 2015).

### 9.3 Populations for Analyses

The analysis populations are specified below. The final decision to exclude participants from any analysis population will be made during a data review meeting prior to database lock.

Analysis Set	Description
Screening (SCR)	All participants, who provided informed consent, regardless of the participant's study intervention status in the study.
Full (FAS)/Safety (SAF)	All participants, who were administered at least one dose of any study intervention.
DLT	All participants treated in the safety run-in period who received at least 75% of the tepotinib and cetuximab planned dose and complete the DLT period (3 weeks after start of treatment with study intervention), or who experience a DLT during the DLT period regardless of the received amount of each study intervention.
PK	All participants, who receive at least one dose of study intervention, have no relevant protocol deviations or important events affecting PK, and provide at least one measurable post-dose concentration. Participants will be analyzed per the actual study intervention they received.
Immunogenicity	All participants who receive at least one dose of study intervention and have at least one valid ADA result. All ADA analyses will be based on this analysis set.

